6.7 Analysis of efficacy

Efficacy will be analysed as described in the clinical trial protocol.

Sensitivity analysis 2 for the primary estimand (secondary endpoints)

In the sensitivity analysis 2 for the primary estimand, the protocol specifies that: "If subjects have withdrawn due to an AE or due to lack of efficacy, they are still considered non-responders". Such subjects will be identified based on their reason for permanent discontinuation of IMP.

Primary analysis of primary estimand (continuous other endpoints)

It is specified in the protocol that the continuous other endpoints will be analysed using a repeated measurements model on the post-baseline responses up to Week 16. Data collected after permanent discontinuation of IMP or after initiation of rescue medication will not be included in the analysis.

However, some subjects may not have any post-baseline data collected before initiation of rescue medication. To ensure that all subjects are included in the analysis, the baseline value

will for these subjects be carried forward as the first post-baseline assessment, corresponding to imputing a change of 0 at the first post-baseline assessment.

Tertiary (composite) estimand (continuous other endpoints)

For the continuous other endpoint ‘Change from baseline to Week 16 in EASI score’ an analysis is introduced where subjects who received rescue medication are considered non-responders. This new analysis aim to estimate the treatment effect for a ‘Composite’ estimand which is currently not pre-specified in the protocol for the continuous other endpoints. Thus, a new tertiary ‘Composite’ estimand for the continuous other endpoints is introduced.

Primary analysis for the tertiary (composite) estimand (continuous other endpoints): Data retrieved at Week 16 for subjects who have permanently discontinued IMP prior to Week 16 will be included in the analysis. Subjects who prior to the Week 16 visit have received rescue medication will be considered non-responders by using worst observation carried forward (including the baseline value).

Missing Week 16 data among subjects who did not use rescue medication will be imputed using MI (100 copies of the dataset, seed=11109941) assuming missing at random (MAR) within arms (based on sequential use of an ANCOVA model for Week 2, 4, 6, .. and 16). For subjects who dropout without any use of rescue medication, missing data at subsequent visits will be imputed under the assumption that the subject adheres to the randomised treatment regimen, i.e. the stepwise imputation model will be estimated based on available data from all subjects but excluding individual subject data captured after initiation of rescue medication or permanent discontinuation of IMP. For each of the 100 imputed datasets, the continuous other endpoint will be analysed using an ANCOVA model with effects of treatment, baseline disease severity (IGA 3 or 4), and baseline value. The estimates and standard errors from the 100 analyses will be combined using Rubin’s rule to form a unique point estimate and standard error.

Multiple imputation

For the analysis of the secondary endpoints, multiple imputation will be carried out as specified in the protocol, using SAS PROC MI. For multiple imputations related to the treatment policy estimand and the hypothetical estimand sensitivity analyses, the seed 11109941 will be used. The remaining seeds are specified in the protocol.

When performing multiple imputation of continuous parameter values, imputed values at visits prior to Week 16 outside the relevant parameter scale shall be used as is. Values imputed

at Week 16 shall be truncated to the nearest upper or lower bound on the given scale. For example, negative imputed EASI values at Week 16 will be set to 0.

For imputation of IGA values, the LIKELIHOOD=AUGMENT option will be used (1).

For imputation of IGA values, it may occur that the observed data from which the imputation model is fitted does not contain all levels of the IGA predictors necessary for the imputation. For example, the imputation model for IGA values at Week 8 will be based on observed data from the subset of subjects with observed IGA values at both Week 6 and Week 8. If only the IGA values (0,1,2,3) are observed at Week 6 in this subset of subjects, the imputation model will not be able to predict IGA values at Week 8 for a subject with an IGA value of 4 at Week 6. To avoid this situation, in this specific example IGA values of 3 and 4 at Week 6 will be combined into a single category for the purpose of the imputation. In general, if this situation arises, IGA categories will be combined into a single category at the specific visit for the purpose of the specific imputation, according to the rules in [Table 2](#).

Table 2: Adjacent IGA categories combined in case of missing predictors in observed data

IGA value(s) missing in imputation model	IGA categories combined
0	(0,1)
1	(0,1)
2	(2,3)
3	(2,3)
4	(3,4)

For the analysis of binary efficacy endpoints, it may for the tertiary (treatment policy) estimand not be possible to conduct a multiple imputation procedure if too few subjects have retrieved data, e.g. at Week 16. In such cases, the analysis may be omitted.

Percentage change in EASI score

In addition to the repeated measurements analysis of absolute reduction in EASI score which was planned in the protocol, the same analysis will be conducted for the percentage change from baseline in EASI scores.

Subgroup analyses

To assess the consistency in response rate across subgroup the following subgroup analyses will be performed for the primary estimand:

- IGA 0/1 at Week 16 by baseline IGA

- EASI75 at Week 16 by baseline IGA

Scoring of PROs

POEM	Scored according to: https://www.nottingham.ac.uk/research/groups/cebd/documents/methodological-resources/poem-for-self-completion.pdf
DLQI	Scored according to: http://sites.cardiff.ac.uk/dermatology/quality-of-life/dermatology-quality-of-life-index-dlqi/dlqi-instructions-for-use-and-scoring/
EQ-5D-5L	Index values calculated according to: https://euroqol.org/eq-5d-instruments/eq-5d-5l-about/valuation-standard-value-sets/crosswalk-index-value-calculator/ The UK value sets will be used.
HADS	The HADS consists of 14 items, 7 of which are related to anxiety and 7 related to depression. The maximum score is 21 for each subscale (anxiety and depression). If 1 question is missing within a subscale, the response to that question will be imputed as the mean of the remaining questions in that subscale. If more than 1 question is missing within a subscale, the subscale is considered missing.

Missing baseline assessments

When the baseline value is missing, endpoints concerning a change from baseline cannot be derived, and such subjects will be excluded from the analysis. Since the missingness of baseline values are unrelated to the assigned treatment, bias should not be a concern with this approach.

6.8 Analysis of safety

6.8.1 Adverse events

AEs will be summarised and listed.

Assignment of AEs to periods

An AE will be assigned to a given period (treatment period or safety follow-up) if the start date is after the start date and before the end date of that period (see Section 6.9.2, Table 6).

For AEs with start day on the same day as the first dose was given, only AEs starting after the first dose was given will be considered treatment-emergent and assigned to the treatment period.

AEs starting on the day of exposure end (as defined in Section 6.9.2) will be assigned to the safety follow-up treatment period.

For handling of incomplete start dates of AEs, see Section 6.9.3.

Sort order of AE tables

Generally, AE tables by system organ class and/or preferred term will be sorted by decreasing number of affected subjects in the Tralokinumab group.

Other adverse events

A MedDRA search on all reported AEs was specified to capture AEs belonging to injection site reactions. The MedDRA search to capture this safety area of interest was performed using the following HLT levels (based on primary and secondary terms): ‘administration site reactions NEC’, ‘application and instillation site reactions’, and ‘injection site reactions.

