## 6 Trial objectives and endpoints

### Panel 3: Objectives and endpoints

Objectives	Endpoints
Primary objective	Primary endpoints
To demonstrate non-inferiority of tralokinumab versus placebo with respect to immune responses to concomitantly administered vaccines.	
 
Positive anti-tetanus response at Week 16 (3-fold IgG increase compared to Week 12 if IgG <math>\leq</math>1.0 IU/mL at Week 12; or IgG <math>\geq</math>2.5 IU/mL if IgG >1.0 IU/mL at Week 12)
 
Positive anti-meningococcal response at Week 16 (IgG <math>\geq</math>3.0 mcg/mL with at least a 3-fold increase compared to Week 12)
 

Secondary objective	Secondary endpoints
To evaluate efficacy of tralokinumab concomitantly administered with vaccines.	
 
IGA score of 0 (clear) or 1 (almost clear) at Week 16
 
EASI75 at Week 16
 

Additional secondary objective	Additional secondary endpoints
To evaluate safety and tolerability of tralokinumab concomitantly administered with vaccines.	
 
Number of AEs
 
Presence of anti-drug antibodies
 

Other objectives	Other endpoints
To evaluate the efficacy of tralokinumab concomitantly administered with vaccines on severity and extent of AD and health-related quality of life.	
 
EASI50 at Week 16
 
EASI90 at Week 16
 
Change from baseline to Week 16 in EASI score
 
SCORAD75 at Week 16
 
SCORAD50 at Week 16
 
Change from baseline to Week 16 in SCORAD
 
Change from baseline to Week 16 in DLQI score
 
Change from baseline to Week 16 in EQ-5D-5L
 
Change from baseline to Week 16 in POEM
 
Change from baseline to Week 16 in HADS
 

AE, adverse event; DLQI, Dermatology Life Quality Index; EASI, Eczema Area and Severity Index; EASI50, at least 50% reduction in EASI score; EASI75, at least 75% reduction in EASI score; EASI90, at least 90% reduction in EASI score; EQ-5D-5L, EuroQoL 5-Dimension Health Questionnaire 5 Level; HADS, Hospital Anxiety and Depression Scale; IGA, Investigator's Global Assessment; POEM, Patient-Oriented Eczema Measure; SAE, serious adverse event; SCORAD, Scoring Atopic Dermatitis; SCORAD50, at least 50% reduction in SCORAD score; SCORAD75, at least 75% reduction in SCORAD score.

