## 7 Trial design

### 7.1 Overall trial design

#### Overview

This is a randomised, double-blinded, placebo-controlled, phase 2 trial in adult subjects with moderate-to-severe AD. The primary objective of the trial is to demonstrate non-inferiority of tralokinumab versus placebo with respect to immune response to concomitantly administered Tdap and meningococcal vaccines. The trial will evaluate the percentage of subjects achieving a positive anti-tetanus response at Week 16 and a positive meningococcal response at Week 16.

The trial will consist of a screening period of 2 to 6 weeks (Weeks -6/-2 to 0), a treatment period of 16 weeks (Weeks 0 to 16) and a 14-week off-treatment follow-up period for the assessment of safety (Weeks 16 to 30). The primary endpoints will be assessed at Week 16, and the final safety assessment will be conducted at Week 30 (end-of-trial visit). Eligible subjects may transfer to the open-label ECZTEND trial (LP0162-1337) at Week 16 or later. An overview of the different parts of the trial is provided in [Panel 1](#).

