#### Treatment period (Week 0 to Week 16)

Following the screening period, approximately 200 subjects will be randomised 1:1 to one of the following groups stratified by disease severity (IGA of 3 or 4):

- Tralokinumab 600 mg (4 mL) at Day 0 (hereinafter “baseline”), then 300 mg (2 mL) Q2W.

- Placebo (4 mL) at baseline, then placebo (2 mL) Q2W.

Subjects will each receive 1 dose of Tdap and meningococcal vaccines given intramuscularly at Week 12.

The last administration of IMP will occur at Week 14.

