### 13.3 Reporting of adverse events

AEs reported by the subject or observed by the investigator must be recorded on the AE form of the eCRF and should be described in the following manner:

The *AE term* must be in precise English medical terminology (that is, not necessarily the exact words used by the subject). Whenever possible, a specific diagnosis should be stated (for example ‘allergic contact dermatitis’).

The *duration* of the AE must be reported by the start date and stop date of the event (it will also be recorded if the event is ongoing). In addition, it will be recorded if the AE started prior to first dose of IMP (tralokinumab/placebo); it will also be recorded if the AE started prior to administration of the vaccines.

AEs must be classified in terms of severity, causality and outcome according to the definitions in [Appendix 2](#).

*Action taken with IMP:* any action taken with IMP as a consequence of the AE must be recorded (dose not changed, dose reduced, dose increased, drug interrupted, drug withdrawn, not applicable, unknown).

*Other action taken:* any other action taken as a result of the AE must be recorded (none, concomitant medication, concurrent procedure).

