### 14.2 Trial analysis sets

All screened subjects will be accounted for in the CTR.

All subjects randomised to treatment are included in the FAS and will be analysed for efficacy up to Week 16. Exclusions from the FAS can be considered in special cases as described in

ICH E9, Section 5.2.1, Full Analysis Set. If it is decided to exclude a randomised subject from the FAS, a justification addressing ICH E9 will be given.

A per protocol analysis set will be defined by excluding subjects from the FAS for whom any of the following conditions apply:

- Receive no treatment with the IMP (vaccines).
- Provide no vaccine data at Week 16.
- Are known to have taken the wrong IMP throughout the treatment period.
- Do not fulfil the inclusion criteria no. 3, 6, 7, 8.
- Meet exclusion criterion related to receipt of other vaccines (that is, exclusion criterion no. 10).
- Initiate systemic rescue treatment prior to Week 10 and who are still treated with or exposed to systemic rescue treatment at Week 10 (that is, Week 10 [visit 8] occurs within 5 half-lives after the last dose of systemic rescue medication).
- Initiate systemic rescue treatment at Week 10 or later.
- Have missed more than 2 doses of tralokinumab/placebo before vaccine administration.
- Have missed any of the last 2 doses of tralokinumab/placebo before vaccine administration (that is, Weeks 8 and 10).

The per protocol analysis set will be used as primary analysis set for the vaccine antibody responses at Week 16 (primary endpoints; Panel 13). For the secondary endpoints (IGA 0/1 and EASI75 at Week 16), the FAS analysis will be considered primary.

A safety analysis set will be defined by excluding subjects from the FAS who received no treatment with IMP.

Based on the above-mentioned rules, the inclusion/exclusion of subjects or subject data from the trial analysis sets will be documented in the statistical analysis plan update before breaking the randomisation code.

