#### **14.3.8.1 Adverse events**

AEs will be coded during the course of the trial according to Medical Dictionary for Regulatory Activities (MedDRA). AEs will be presented by preferred terms and primary system organ class (SOC).

Treatment-emergent AEs will be summarised, however, all AEs recorded during the course of the trial will be included in the subject data listings. An event will be considered treatment-emergent if started after the first use of IMP or if started before the first use of IMP (applicable if subject had a wash-out) and worsened in severity thereafter. The tabulations described in the following will only include the treatment-emergent events. In each of the tabulations, AEs will be defined by MedDRA preferred terms within primary SOC.

An overall summary of the number of treatment-emergent AEs, number (percentage) of subjects with any treatment-emergent AEs, SAEs, deaths, premature discontinuations from the trial due to AEs, treatment-related AEs and severe AEs will be presented.

The number of AEs and the number of subjects experiencing each type of AE will be tabulated by treatment group. The percentage of subjects with AEs will be compared between treatment groups by a chi-square test or Fisher's exact test (if expected cell count < 5).

The severity for each type of AE will be tabulated by treatment group.

The causal relationship to IMP (tralokinumab/placebo) for each type of AE will be tabulated by treatment group. Related AEs are defined as AEs for which the investigator has not described the causal relationship to IMP as 'not related'. The number of related AEs and the number of subjects experiencing each type of related AE will be tabulated. The percentage of subjects with related AEs will be compared between treatment groups by a chi-square test or Fisher's exact test (if expected cell count <5).

The causal relationship to IMP (each vaccine) for each type of AE will be tabulated by treatment group. Related AEs are defined as AEs for which the investigator has not described the causal relationship to IMP as 'not related'. The number of related AEs and the number of subjects experiencing each type of related AE will be tabulated. The percentage of subjects with related AEs will be compared between treatment groups by a chi-square test or Fisher's exact test (if expected cell count <5).

SAEs and AESIs will be evaluated separately and a narrative for each will be given. AEs leading to withdrawal from trial will be listed.

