6.9.2 Definition of trial periods and date of permanent discontinuation of IMP

Date of permanent discontinuation of IMP (tralokinumab/placebo)

Defined for subjects who have a reason for permanent discontinuation of IMP (tralokinumab/placebo) recorded.

Defined as the latest of date of early termination visit (if existing) or date of onset of latest AE leading to withdrawal of trial product, otherwise date of the last visit, excluding safety follow-up and nominal Week 16 visits.

Exposure start

Date and time of first dose.

Exposure end

Date of Week 16 visit (if existing) at time 23:59:00, otherwise date of permanent discontinuation of IMP (tralokinumab/placebo) at time 23:59:00.

Trial periods

The time from exposure start to exposure end will be assigned to the treatment period and remaining time after exposure end will be assigned to the safety follow-up period as shown in [Table 6](#) (ADaM variable APHASE). The ADaM variable APERIODC will indicate the latest treatment at any given time point, thus not including a follow-up period ([Table 7](#)).

Table 6: Start and end time of trial periods (ADaM variable APHASE)

APHASE	Start of period	End of period (only if start date exists)
Treatment period	Exposure start	Exposure end
Safety follow-up period ¹	Exposure end (plus 1 second)	Date of safety follow-up visit (if existing) at time 23:59:00 else Date of last contact at time 23:59:00

1) Only applicable if date of last contact is not equal to date of exposure end.

Table 7: Start and end time of trial periods (ADaM variable APERIODC)

APERIODC	Start of period	End of period (only if start date exists)
-----------------	------------------------	--

Treatment period	Exposure start	Date of last contact at time 23:59:00
------------------	----------------	---------------------------------------

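### No all-cause adverse event comparison starts at vaccination, although the safety objective concerns tralokinumab given with vaccines

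*SAP*

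**What the plan says.** Protocol section 6 (Panel 3) gives the additional secondary objective as "To evaluate safety and tolerability of tralokinumab concomitantly administered with vaccines". Its endpoints are the number of AEs and the presence of anti-drug antibodies. On timing, Protocol 7.1 says "Subjects will each receive 1 dose of Tdap and meningococcal vaccines given intramuscularly at Week 12".

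The AE rules are anchored elsewhere:

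- Protocol 14.3.8.1: "An event will be considered treatment-emergent if started after the first use of IMP". That means Day 0.
- SAP 6.8.1, in part: "An AE will be assigned to a given period (treatment period or safety follow-up) if the start date is after the start date and before". Onset is thus compared with the two limits of each period.
- SAP 6.9.2 sets exposure end as "Date of Week 16 visit (if existing) at time 23:59:00", or otherwise the date of permanent discontinuation. Follow-up begins after that.
- Protocol 14.2: "A safety analysis set will be defined by excluding subjects from the FAS who received no treatment with IMP". SAP section 5 likewise takes all randomised and exposed subjects. Neither requires vaccination.

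Two outputs do look past vaccination. Protocol 14.3.8.1 tabulates AEs by relationship to each vaccine and tests the percentage of subjects with related AEs between arms (chi-square or Fisher's exact). SAP section 5 adds a safety follow-up set for AEs after exposure end.

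Timing data are collected. Protocol 13.3 says of each AE that "it will also be recorded if the AE started prior to administration of the vaccines", and Protocol 9.8.3 has the date and time of each vaccine entered in the eCRF. No specified AE analysis uses either.

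**The concern.** The objective names co-administration with vaccines, yet the main AE tables run from first dose to Week 16 and are mostly made of time before any vaccine. An excess of events on tralokinumab that appeared only after vaccination would be mixed with 12 weeks of earlier events.

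The vaccine-related table does not fully replace an all-cause table. It depends on the investigator's causality opinion. In Protocol Appendix 2, both related categories list a known pattern of response, and the not-related category lists the absence of one. An unexpected drug-vaccine effect is therefore the kind most at risk of being called not related.

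No separate denominator is stated for that table. Subjects who left before Week 12 would then count in the percentages although they could not have had a vaccine-related event.

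**Working it through.** **Plan's own figures.** The documents give no AE rate and no power for any safety comparison, so there is nothing to reproduce on this point. The sample-size figures in Protocol 14.1 (98% and about 89%) do reproduce, at 97.7% and 88.8%, but concern other endpoints.

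**Timing** (Protocol 7.1; visit windows of ±3 days from Panel 2).

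- Share of the treatment period before vaccination: 12/16 = 75%.
- With the windows: 81/115 = 70% to 87/109 = 80%.
- Scheduled time after vaccination: 30 − 12 = 18 weeks. Of these, 4 fall in the treatment period and 14 in off-treatment follow-up.

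**Illustration 1: dilution of any-AE incidence.** Assumptions: constant hazard, 65% of subjects with any AE over 16 weeks on placebo, and the hazard doubled on tralokinumab after vaccination only. The 16-week event-free proportion on placebo is 0.35.

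| | Placebo | Tralokinumab | Difference |
|---|---|---|---|
| Weeks 12–16 | 1 − 0.35^0.25 = 23.1% | 1 − 0.35^0.5 = 40.8% | 17.7 points |
| Weeks 0–16 | 65.0% | 1 − 0.35^0.75 × 0.35^0.5 = 73.1% | 8.1 points |

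On event counts, the same doubling gives (12 + 2 × 4)/16 = 20/16, a 25% excess over 16 weeks against 100% in the window.

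**Illustration 2: chance of seeing a difference.** Assumptions: 4-week post-vaccination risk of 20% against 40%, equal risk q in both arms over Weeks 0–12, 100 subjects per arm of whom 90 are vaccinated, two-sided 5%. The pooled risk is 1 − (1 − q)(1 − 0.9p), where p is the post-vaccination risk. For q = 30% this gives 1 − 0.7 × 0.82 = 42.6% and 1 − 0.7 × 0.64 = 55.2%.

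| Comparison | Difference | Power |
|---|---|---|
| Post-vaccination window, vaccinated subjects | 20 points | about 84% |
| Weeks 0–16, q = 30% | 12.6 points | about 43% |
| Weeks 0–16, q = 50% | 9.0 points | about 26% |
| Weeks 0–16, q = 60% | 7.2 points | about 20% |

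With 80 vaccinated per arm, the window has about 79% power and the pooled comparison about 35%, 21% and 16%.

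**Denominator.** If a fraction f of the safety set was never vaccinated, a true vaccine-related percentage r is printed as r(1 − f). For r = 10%, f = 10% prints 9% and f = 20% prints 8%. The documents do not give f. Protocol 14.1 anticipates 160 of 200 subjects in the per protocol set, which leaves 20% for exclusions of every kind, so f = 20% would use up that whole allowance.

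**The case against.** A reader might infer that post-vaccination safety is never compared between the arms. The documents do not support that. Protocol 14.3.8.1 tests vaccine-related AEs between arms, such events can only follow vaccination, and the SAP supplements this without withdrawing it. Related means anything not recorded as not related, which is a broad net in a double-blind trial. For vaccinated subjects the follow-up set is also wholly post-vaccination and covers 14 of the 18 scheduled weeks.

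Other parts of the defence also carry weight:

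- Panel 3 uses the same wording about concomitant vaccines for its efficacy objectives, whose endpoints include changes measured from baseline. The phrase can describe the whole regimen. The listed safety endpoint is the number of AEs, with no window, and the plan delivers it.
- Any-AE incidence saturates, so illustration 1 shows more shrinkage than event counts would. Tables by preferred term would also show an event type that arises only after vaccination.
- The counts of related AEs and of affected subjects do not depend on the denominator. Distortion between arms needs unequal drop-out before Week 12, for which no figure exists.
- A vaccinated-only set conditions on something that happens after randomisation.

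All of this limits the point but does not remove it. The causality table can miss events judged unrelated. Follow-up is off treatment, starts four weeks after vaccination, loses subjects who transfer to the extension trial, and has no between-arm test of its own described. The Week 12–16 window on treatment, where co-administration takes place, is left without an all-cause comparison.

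**Conclusion.** The plan specifies no all-cause AE comparison anchored to vaccination among vaccinated subjects, although the onset flag is collected. Post-vaccination safety is compared between arms only through AEs judged related to a vaccine, and is otherwise covered by the follow-up summaries. The related-AE percentages can be understated by never-vaccinated subjects in the denominator.

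The 75% is firm, apart from the visit windows. The dilution, power and understatement figures are illustrations under assumed rates and show direction, not expected size. It would go too far to conclude that the safety endpoint fails or that the safety comparison is biased: the listed endpoint is delivered, and nothing in the documents indicates unequal early drop-out. This is an inexpensive improvement that would let the trial address its own safety objective more directly. No primary or efficacy conclusion depends on it.

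**What to change.** In SAP sections 5 and 6.8.1:

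1. Define a vaccinated safety set: safety-set subjects who received at least one trial vaccine. Report the number vaccinated by arm.
2. Add a descriptive by-arm table of AEs, serious AEs and AEs of special interest with onset from vaccine administration to exposure end in that set. Use the vaccine date and time, with the onset flag to settle incomplete onset dates and same-day events.
3. For each vaccine's related-AE percentages, use the subjects who received that vaccine as the denominator.
4. Keep the existing 16-week and follow-up tables.

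The cost is SAP wording and a few tables, with no new data. The new set is defined by a post-randomisation event, so the comparison should be labelled supportive.

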### **Long-term extension trial**

Eligible subjects may be invited to enter an open-label, long-term extension trial conducted under a separate protocol (LP0162-1337, ECZTEND). Subjects who fulfil the eligibility criteria in the ECZTEND protocol can enter the trial at the Week 16 visit or up to 16 weeks after the last IMP injection in the present trial. Subjects who transfer to ECZTEND must have had their Week 16 visit under the current protocol (LP0162-1341).

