The safety analysis set comprises all subjects randomised to treatment who were exposed to IMP. The protocol further specifies to exclude subjects from the safety analysis set for whom no post-baseline safety data are available. However, since all subjects receive the first dose of IMP in connection with the Week 0 visit and are subsequently monitored for immediate drug reactions, all exposed subjects are considered to have post-baseline safety data available and no such further exclusions will be made.

In addition to the analysis sets defined in the protocol, a safety follow-up analysis set will be used as the basis for evaluation of adverse events during the safety follow-up period. It comprises all subjects for whom date of last contact is after the date of exposure end, where exposure end is defined as the Week 16 visit for subjects completing the treatment period, and otherwise the date of permanent discontinuation of IMP (tralokinumab/placebo) for subjects not completing the treatment period. See also Section 6.9.2 for further details.

For analysis of efficacy, subjects will be included 'as randomised'.

For analysis of safety, if a subject is mistakenly given an IMP other than that to which they were randomised, they will be analysed 'as treated', thus included in the group according to the therapy actually received by the subject. The below rules will be applied.

Subjects who received at least one dose of tralokinumab will be analysed in the tralokinumab treatment group. Although this may dilute the AE rate in the tralokinumab treatment group slightly by including in the denominator subjects who only received one dose of active treatment, it will ensure that no significant drug reactions to tralokinumab will erroneously be assigned to placebo.

The definition of the per protocol analysis set as described in the protocol has been updated to accept negligible deviations in baseline disease severity related to the EASI status. Thus, the criteria from inclusion criterion 7 have been modified to require an EASI score of ≥ 12 at screening OR ≥ 16 at baseline instead of requiring both criteria to be met. The rationale for this change is that marginal deviations in baseline disease severity is not considered to affect the vaccine response.

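### SAP 6.8.1 counts AEs that start on the exposure-end day as follow-up, while Table 6 keeps that day in treatment; for subjects with no later contact such AEs have no by-period (APHASE) assignment

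*SAP*

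**What the plan says.** SAP 6.8.1 gives a general rule and a boundary rule. Under the general rule, with a reference to Table 6, an AE belongs to a period "if the start date is after the start date and before the end date of that period". The boundary rule adds that "AEs starting on the day of exposure end (as defined in Section 6.9.2) will be assigned to the safety follow-up treatment period".

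SAP 6.9.2 defines exposure end as "Date of Week 16 visit (if existing) at time 23:59:00, otherwise date of permanent discontinuation of IMP (tralokinumab/placebo) at time 23:59:00". Table 6 gives the time up to that moment to the treatment period and starts safety follow-up one second after it. For the date of permanent discontinuation, 6.9.2 reads: "Defined as the latest of date of early termination visit (if existing) or date of onset of latest AE leading to withdrawal of trial product". If neither date exists, the last visit date is used.

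Footnote 1 of Table 6 limits the follow-up period: "Only applicable if date of last contact is not equal to date of exposure end". SAP section 5 defines the safety follow-up analysis set in the same way: "It comprises all subjects for whom date of last contact is after the date of exposure end". Under protocol 7.1, subjects eligible for ECZTEND "can enter the trial at the Week 16 visit or up to 16 weeks after the last IMP injection in the present trial".

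**The concern.** The boundary rule and Table 6 place the same calendar day in different periods, although 6.8.1 cites Table 6 as its source. SAP section 5 makes the safety follow-up set the basis for evaluating follow-up AEs. Period assignment therefore decides which by-period table and which denominator an AE enters. Two programmers could each follow the SAP and produce different tables.

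Two situations matter. First, the AE that ended treatment can be reported as a follow-up event when its onset date is the exposure-end date. Second, an AE on that day in a subject with no later contact is directed to a follow-up period that the subject does not have, and the SAP states no fallback. In addition, exposure time (SAP 6.5, using 6.9.2) counts that day as treatment exposure while its AEs are counted as follow-up.

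**Working it through.** The plan gives no figure to reproduce, so the rules are first applied to individual subject patterns and the size is then bounded.

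**Step 1: the exposure-end date.** Day 0 is the first dose, and Week 16 falls on Day 7 × 16 = 112. SAP section 5 uses the Week 16 visit for subjects who complete treatment and the discontinuation date for the others. That date is the later of the early termination (ET) visit and the onset of the latest withdrawal AE. It therefore equals the AE's own onset date when there is no ET visit, or when onset is on or after that visit.

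**Step 2: apply each rule.** In the first four rows the AE starts on the exposure-end day.

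| Pattern | Table 6 clock times | General rule, dates only | Boundary rule in 6.8.1 |
|---|---|---|---|
| Completer with follow-up, AE on Day 112 | Treatment | Neither | Follow-up |
| Roll-over with last contact on Day 112, AE on Day 112 | Treatment | Neither | Follow-up, but no such period exists and the subject is outside the follow-up set |
| Withdrawal AE sets discontinuation, no ET visit, later safety visit | Treatment | Neither | Follow-up |
| Withdrawal AE on the ET visit day, no later contact | Treatment | Neither | Follow-up, but no such period exists |
| Withdrawal AE before the ET visit | Treatment | Treatment | Does not apply |

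The last row has no conflict. Read by date, the strict upper limit in the general rule also leaves the last follow-up day (for example Day 210) unassigned.

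**Step 3: size.** Day 0 to Day 112 is 113 calendar days. Assuming even onset, the share of treatment-period AEs starting on the exposure-end day is 1/113 = 0.885%.

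The documents give no AE total. Assume 1 to 3 AEs per subject in 200 randomised subjects, that is 200 to 600:

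- 200/113 = 1.8 AEs
- 600/113 = 5.3 AEs

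Assume also that 25% to 75% of subjects roll over with last contact on that day (not in the documents):

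- 1.8 × 0.25 = 0.4 AEs
- 5.3 × 0.75 = 4.0 AEs

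So about 2 to 5 AEs move to follow-up, and about 0.4 to 4 of these have no APHASE period.

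**Step 4: what does not change.** Protocol 14.3.8.1 sets no upper time limit: "An event will be considered treatment-emergent if started after the first use of IMP". The affected AEs stay treatment-emergent, stay in the overall counts and are listed.

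**The case against.** The strongest reply is that the boundary sentence is a deliberate tie-break. Protocol 13.3 records AE start and stop dates and lists no clock time. Read by date, the general rule leaves the exposure-end day unassigned, and the next sentence fills that gap; a specific rule governs over a general one. The last dose is at Week 14, so treating the Week 16 day as follow-up is not absurd, and the rule is the same in both arms. This settles the order of the rules for subjects with later contact. It does not create a follow-up period for those whom footnote 1 leaves without one, and it leaves Table 6 and exposure time in disagreement with the AE assignment.

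A second reply is that Table 7 (APERIODC) runs treatment to last contact, so these AEs do have a period there. That is correct, and the gap is one of APHASE only. But 6.8.1 refers to Table 6, and APERIODC has no follow-up period at all.

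A third reply is that the withdrawal-AE result is rarely seen. Protocol 10.3 asks subjects who discontinue to attend an ET visit, such AEs usually start before it, and protocol 14.3.8.1 lists AEs leading to withdrawal without a split by period. This stands, and it keeps the effect small.

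The count is also uncertain in both directions. AEs starting later that day in a subject whose last contact was the visit may never be captured, so a full day's share may be too high. Against that, Week 16 includes physical examination, ECG, vital signs and laboratory tests, and clinically significant abnormal findings are reported as AEs, which could cluster onsets on that date.

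**Conclusion.** The concern holds. SAP 6.8.1 and Table 6 assign the exposure-end day differently, and subjects whose last contact is that day have no period to receive the AE. Same-day roll-over to ECZTEND makes this a foreseeable group. A withdrawal AE is misplaced only when its onset date is the exposure-end date.

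The estimate of about 2 to 5 AEs moved, with about 0.4 to 4 lacking an APHASE period, rests on even onset, the assumed AE total and the assumed roll-over share. No efficacy or primary result is affected, and the effect is limited to tables split by APHASE. The correction should still be made: the rule as written misassigns events, and changing it is nearly free.

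**What to change.** Replace the boundary sentence in SAP 6.8.1 with:

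> An AE whose start date equals the exposure-end date belongs to the treatment period.

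Restate the general rule by date:

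> Treatment period: onset after the first dose, and on a date no later than the exposure-end date. Safety follow-up: onset on a date later than the exposure-end date and no later than the last date of the follow-up period.

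This agrees with Table 6 and with exposure time, and it covers the last follow-up day. The date rules were run day by day on six subject patterns: completer; same-day roll-over; discontinued without an ET visit, with and without later contact; and withdrawal AE before and after the ET visit. No day was unassigned or assigned twice.

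The cost is two SAP sentences and one date comparison in the AE dataset. Table 6 and the analysis sets need no change for this point. One separate gap remains: Table 6 ends follow-up at the safety follow-up visit even if last contact is later, so an AE between those dates is still unassigned.
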